### **6.5 Special circumstances**

The study team will counsel participants on safe use of their wearable device in accordance with the manufacturer's instructions. This will include circumstances when the device should be removed and any side effects the participant may experience. Participants will be provided with contact details for the study team so that they can contact the team if they have questions. This will be an email address and phone number through which the research team will be contactable 09:00-17:00 Monday to Friday.

### **6.6 Training and support for participants**

Participants will be given detailed instructions on their wearable device and initial troubleshooting will be provided. Participants will be provided with a telephone number and study email address should they have any difficulties using their device or interacting with the software.

There is a small possibility that the participant may become concerned when reviewing their own vital sign data on their smart device. In this case the participants will be encouraged to contact the research team via telephone and/or email address. Participants will then be signposted to the appropriate service if necessary. In some cases, participants will be able to show their device data on their smart phone to their primary care physician, if required.

## 7) OUTCOME MEASURES

This is a feasibility study, the results of which will inform the development and planning of a much larger clinical study into prehabilitation in live renal transplant patients and the use of wearable technology to augment this. The hypothesis is that prehabilitation may have a significant positive impact on the outcomes for recipients and donors in live kidney transplants.

This study will examine the interaction between participants and the prehabilitation exercise videos, the set up for this additional service within the transplantation team and test the methods of data extraction.

This study will perform data analysis which may show benefit of prehabilitation for kidney transplant recipients and live donors, although this is not powered.

## 8) DATA COLLECTION, SOURCE DATA AND CONFIDENTIALITY

### 8.1 Recruitment

Consent to contact, screening proformas, consent forms, all questionnaires and patient journals will be retained in the study documentation. A copy of consent form will also be uploaded to their electronic patient records.

### 8.2 Questionnaires

Questionnaires will be completed in writing. Questionnaires will then be stored with the study information by the PI in a locked cabinet. After completion of the questionnaire these will be given to the PI at the earliest opportunity. Answers from the questionnaire will be transcribed into pseudonymised data collection tools.

### 8.3 Data Extraction

Demographics, current and past medical history, social status, planned operation date, medications, GP information and operation notes will be accessed through electronic patient records with their informed consent. This data will be pseudonymised and linked to their assigned study ID only. At the end of the study, when full data collection is complete study IDs will be removed, and data fully anonymised prior to analysis.

### 8.4 Oura ring/Withings watch/Corsano wristband

Only relevant data from the participant's wearable device will be accessed from the Cloud by a member of the research team with their informed consent. Relevant data includes

biometric (heart rate, heart rate variability, respiratory rate, blood pressure, SpO2, core body temperature), activity (step and workout count) and sleep data.

#### 8.5 Data Management

- Participants will be assigned a study ID at the time of informed consent taking, only known to the research team. A key linking personalised details (name and NHS number) to the study ID will be stored as an encrypted file on NHS Trust platform, only available to those in the research team.
- Data will be pseudonymised via the individual ID whilst data collection for this study is being conducted
- Data will be fully anonymised after data collection has been completed and the ID key permanently deleted.
- Anonymised data from this study will be held by the principal investigator for 5 years after the completion of this study.
- Data will be held under password protected files on password protected NHS trust computers.
- Only data pertinent to this study (mentioned above) will be extracted from the wearable devices via the Cloud.
- Following return of devices at the end of participant involvement, they will be restored to factory settings.
- No hard or soft data copies will be transferred to University of Manchester (UoM).
- Study data and materials may be looked at by UoM individuals, from regulatory authorities or the NHS trust for monitoring and auditing purposes.

### 9) STATISTICAL CONSIDERATIONS

#### 9.1 Statistical Analysis

##### 9.11 Study analysis

All variables will be explored descriptively with graphs and summary statistics. Key characteristics, such as overall recruitment, compliance with the prehabilitation programme and qualitative analysis of responses to open questions will be used to assess the primary research question.

Description analysis will be performed on all appropriate variables, within the limits of an unpowered study. This will include number (%), mean, median, maximum and minimum values, standard deviation and interquartile range.

The number of potential participants screened, the number enrolled, withdrawals and completion of study will all be listed outcomes.

Qualitative values, such as post operative complications will be listed.

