This study will provide key information into how the set-up of the trial and delivery of this service will be met. The study is not powered to detect statistically significant differences in outcome of the two groups, although statistical analysis will be performed to determine whether the impact of this intervention on its participants has led to a measurable change in physiological and clinical outcomes. This study provides the opportunity to test the set-up of a new team, and how the wearable technology can be utilised in this cohort of patients.

We will assess 4 key areas (18). First, we will evaluate the recruitment capability through the transplant team at MRI. This determines the ability and expected speed of recruitment of a much larger study. Secondly, this will evaluate and refine our data collection procedure in terms of data extraction, time for data collection and inform the need for future grants for research staff to be allocated time for OPERATE. Thirdly, this will evaluate the acceptability

and suitability of the intervention. As already discussed, exercise interventions for prehabilitation programmes have struggled previously with finding an acceptable method of exercise intervention, particularly one which participants will remain compliant with. Finally, this will provide a preliminary evaluation of participant responses to the intervention, in terms of improved post operative outcomes and patient satisfaction (18,19). Each of these key areas will provide important actionable information that will lead to a more refined and improved larger study, thereby saving time, funding, and limiting wasteful interaction with participants in the future (20).

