### **Withdrawal from study**

The reasons why participants will be withdrawn from the study are as follows:

- Participant's decision to withdraw from the study
- Investigator decision
- Safety reasons
- Severe non-compliance to protocol as judged by the investigator (participating in less than 50% of exercise sessions as monitored by their diary and wearable technology).

If a participant decides to withdraw:

- Monitoring with the wearable device will cease.
- Participants will continue with the normal standard of care.

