### Contact 5: Completion of prehabilitation programme

On admission to hospital the participants will repeat the hand grip strength test and complete a questionnaire on how they feel the prehabilitation programme has gone. Wearable devices will be removed during their inpatient stay and reapplied on discharge for a further 6 weeks of monitoring.

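### Section 3 promises to determine whether participants changed, but Section 9.11 plans only per-variable summaries, which do not estimate change

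*Protocol*

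**What the plan says.** The last part of Section 3 (Background) first disclaims power: "The study is not powered to detect statistically significant differences in outcome of the two groups". The same sentence then commits to more than description: "statistical analysis will be performed to determine whether the impact of this intervention on its participants has led to a measurable change". The outcomes it goes on to name are physiological and clinical.

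Section 9.11 is the only place where quantitative analysis is set out. It opens with "All variables will be explored descriptively with graphs and summary statistics", and continues: "Description analysis will be performed on all appropriate variables, within the limits of an unpowered study". Of the summaries it says: "This will include number (%), mean, median, maximum and minimum values, standard deviation and interquartile range". Withdrawals and completions are to be listed, and so are post-operative complications.

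Repeated measurements are collected. Grip strength is taken at set-up, and Appendix 1 (Contact 5) says: "On admission to hospital the participants will repeat the hand grip strength test". Section 5.2 provides two weeks of wearable data before the programme, then wear during the programme and again after discharge.

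Several rules govern who leaves. The withdrawal list in Section 6.4 includes severe non-compliance, defined as "participating in less than 50% of exercise sessions as monitored by their diary and wearable technology". Under Section 6, a participant who meets an exclusion criterion after enrolment is removed, and Section 6.2 counts inability to take part in the exercise programme as such a criterion. Section 6.4 lets people who withdraw consent agree that data already collected be used. Section 8.3 removes study IDs before analysis.

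**The concern.** A promise to determine change needs an estimate of change. A mean and SD for each variable at each time do not give one. They do not show how far individuals moved, and they carry no interval for the movement.

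A reader of the report would naturally subtract one group mean from the other. If the two means come from different sets of people, that difference combines individual change with the effect of who left. The results are meant to support a grant application for a larger study (Section 2), so an apparent gain produced by drop-out could be carried into its planning.

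The clinical half of the promise has a different problem. Post-operative complications have no pre-operative value, and there is no control group, so the study has nothing against which to measure a change in them.

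**Working it through.** There is no planned figure to reproduce: Section 9.2 states that no power calculation was made. The check compares the texts and then uses illustrative arithmetic.

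**1. Promise against method.** Section 3 promises a determination of change. Section 9.11 offers count, percentage, centre, spread and range for each variable. No change score, pairing, interval or set of participants for a before-after comparison appears.

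**2. Who is measured at each time.** Four sessions a week for six weeks is 4 × 6 = 24 sessions, so the compliance rule removes anyone with fewer than 12. Wearable monitoring stops for those who decide to withdraw. The provision for keeping earlier data is written for withdrawal of consent, and the protocol does not say what happens to the data of people removed by rule. The number at baseline can therefore exceed the number at admission, but need not. Section 3 itself links poor compliance to fatigue, deconditioning and poor mobility, which makes loss related to fitness plausible.

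**3. Possible size of the artefact.** Let f be the fraction lost and g the baseline gap between stayers and leavers. With no individual change, the group mean shifts by s = f × g. Losing 3 of 10 gives:
- g = 3 kg: 0.3 × 3 = 0.9 kg
- g = 6 kg: 0.3 × 6 = 1.8 kg
- g = 10 kg: 0.3 × 10 = 3.0 kg

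In baseline SD units, a simulation with 20 participants, unchanged individual values and 40,000 runs gave:

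| Loss | 10% lost | 20% lost | 30% lost |
|---|---|---|---|
| Weakest leave | 0.18 | 0.33 | 0.48 |
| Loss correlated 0.5 with baseline | 0.09 | 0.17 | 0.24 |
| Random | 0 | 0 | 0 |

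Every loss rate, gap and correlation here is an assumption.

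**4. What within-participant change does to the bias.** Suppose loss depends on the measured baseline value, the before-after correlation is r, and there is no true average change. The difference in group means is then biased by r × s, and the mean change among completers by −(1 − r) × s (regression to the mean). For s = 1.8 kg:
- r = 0.8: 0.8 × 1.8 = +1.44 kg against −0.2 × 1.8 = −0.36 kg
- r = 0.5: 0.5 × 1.8 = +0.9 kg against −0.5 × 1.8 = −0.9 kg

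If loss depends only on stable underlying fitness, the completer bias disappears.

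**5. Precision of the change.** The 95% half-width for m pairs is t(m − 1) × √(2(1 − r)/m), in SD units. With all 10 in a role and r = 0.8 it is 2.262 × √(0.4/10) = 0.45 SD. With the 7 left after losing 3 it is 2.447 × √(0.4/7) = 0.58 SD. For 7 pairs it is 2.447 × √(1/7) = 0.92 SD at r = 0.5 and 2.447 × √(0.2/7) = 0.41 SD at r = 0.9. The interval is wide but informative for planning.

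**The case against.** The strongest reply is that change scores, analysis sets and intervals usually belong in a statistical analysis plan, and one may exist. That holds for the detail. It does not remove the mismatch between two statements in the protocol itself, one promising a determination and the other planning only summaries.

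A reader might go further and infer that Section 9.11 estimates change wrongly. The text does not support that. It nowhere says that baseline and admission means will be compared, and a change in grip strength could count among the variables it considers appropriate. The fault is that the estimate is left unspecified.

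A reader might also infer that weaker participants will be the ones lost. The compliance rule selects on sessions completed, not strength, and Section 3 describes donors as free of any baseline medical condition. The link is plausible, mainly for recipients, but it is an inference. Section 9.11 does list withdrawals, so attrition will be visible.

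Two further points stand. Completer change is not free of bias: at r = 0.5 the regression effect is as large as the artefact it replaces, with the opposite sign. And a change in clinical outcomes need not mean a before-after difference within a person, so that part is mainly a matter of wording.

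**Conclusion.** The mismatch is real and rests on the protocol's own text: Section 3 states an aim that the summaries in Section 9.11 do not meet, although the data to meet it for physiological measures are collected. The bias is conditional. It arises only if the two time points are summarised on different people, their difference is read as change, and loss is related to fitness. The removal rules allow the first and make the last plausible, but prove neither.

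Its size cannot be stated from the documents. The illustrations run from zero under random loss to about half an SD if the weakest 30% leave, and to 1.8 kg in the worked case of 3 lost with a 6 kg gap.

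The primary question is feasibility, judged on recruitment, compliance and qualitative responses, and it is unaffected. Descriptive analysis suits such a study and no hypothesis test is called for. This is a cheap improvement worth making, not a threat to the main conclusion.

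**What to change.** In Section 9.11, state that:
- for variables measured before and after the programme (grip strength and the wearable biometric, activity and sleep measures), within-participant change will be summarised separately for donors and recipients, with a 95% confidence interval, among those with both measurements;
- the wearable follow-up window will be named, because wear after discharge follows surgery as well as the programme;
- baseline values of participants without a second measurement will be shown alongside those of participants with one;
- each participant's time points will stay joined when study IDs are removed under Section 8.3.

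In Section 3, confine the statement about measurable change to these physiological measures, and describe post-operative clinical outcomes as descriptive summaries.

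The cost is a few sentences and a small amount of extra analysis, with no new data. The limits should be stated too: change is reported on fewer people than the baseline table, completer change may carry some regression to the mean and need not represent everyone enrolled, and without a control group it cannot be attributed to the programme.

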#### **9.12 Thematic Analysis**

Where possible, depending on the quality and quantity of responses, anonymised free text answers to questionnaires or direct quotes from patient journals will be analysed through thematic analysis. The framework method will be used to examine for themes within participants responses (27). This involves the researcher immersing themselves in the data to familiarise themselves. Next themes and codes will be drawn from the data before charting and summarising the data. A matrix will be used to summarise the data before interpretations are drawn from this. This analysis will then be included in the write up with anonymised quotations, where suitable.

#### **9.2 Sample Size:**

This is a feasibility study to assess the role and interaction between prehabilitation services prior to transplantation and the use of wearable technology to augment this. Therefore, a power equation has not been used. The results of this study and its feasibility will indicate the need and success of a successive powered study. A provisional sample size of 10 donors and 10 recipients of live renal transplantation has been deemed suitable to determine the success of a successive trial. This is in part limited by the availability of wearable devices to run this study.

### **10) MONITORING AND QUALITY ASSURANCE**

The responsibility for monitoring the study and its quality assurance is the chief investigator (CI) [name]. Vital sign data will be monitored and commented upon at two-week intervals as per the study protocol. Each participant will be closely monitored by the transplant team, as per their usual standard of care. The research team will meet every 3 months to monitor the study for recruitment and discussion of any adverse events.

### **11) SAFETY CONSIDERATIONS AND ADVERSE EVENTS**

Adverse events (AEs) will be recorded by investigators during any face-to-face interactions and during the fortnightly telephone reviews. These events will be documented on the CRF and reported to the CI. Participants will be requested to contact the research team via

phone or email to highlight any AEs that arise between interactions. The research team will meet to discuss AEs every 3 months, or sooner should any urgent safety measures arise.

Possible adverse events (as per separate risk assessment):

- Localised skin irritation or dermatitis
- Injury, exacerbation of underlying medical condition, slip or fall
- Inappropriate fit, catching environment/clothing
- Minor electric shock

Any new underlying pathology that is identified through this study will be highlighted to the transplant team that is primarily involved in the patients care.

Participants will be advised that they should stop exercising if they begin to feel unwell, that they let someone know and take usual medications as appropriate (such as salbutamol inhaler or GTN spray if they are already prescribed them), and to call 999 if none of the above help. This is the same as a participant would do if exerting themselves during their normal activities.

The CI is responsible for:

1. Receiving and assessing AEs and adverse reactions, noted by the research or clinical teams
2. Reporting AEs and urgent safety measures to the sponsor and REC as per the requirements of the Research Ethics Service
3. Maintaining a log of AEs occurring during the study and making this available to the sponsor on request.

Cutoff date for recording of SAEs will be at the participant 6-week post-operative follow up outpatient appointment when wearable devices will be removed and returned to the clinical team.

## **12) PEER REVIEW**

Input for the design of this study has been taken from the prehab for cancer (P4C) team from their varied experience in setting up prehabilitation services for patients awaiting cancer related surgery in the Northwest, whilst wearing Oura ring and Withings watches.

## **13) ETHICAL and REGULATORY CONSIDERATIONS**

### **13.1 Approvals**

NHS REC and HRA approval will be obtained before commencing research. The study will be conducted in full conformance with all relevant legal requirements and the principles of the

Declaration of Helsinki, Good Clinical Practice (GCP) and the UK Policy Framework for Health and Social Care Research 2017.

### **13.2 Risks**

#### **13.21 Risk related to exercise**

Risks to participants will be minimised by careful selection criteria. Those at risk of cardiac ischaemia or arrhythmia are excluded from this study as participants will be undertaking unsupervised exercise. Each participant will complete an initial questionnaire to assess their baseline fitness and decide on the level of prehabilitation exercise video they should follow. Participants will be given information of when they should stop exercise (such as chest pain and excessive shortness of breath) and when to call for help.

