## 2) INTRODUCTION

This is a feasibility study to investigate the effectiveness of a prehabilitation programme for live renal transplantation donors and transplant recipients. Participants will undergo a 6 week, at home exercise programme prior to their procedure. This programme of prehabilitation will be monitored using an exercise diary and wearable technology. The data will be utilised, along with participant feedback to assess their compliance and physiological effects of the exercise regimen.

This study will inform the research group on the feasibility of bespoke prehabilitation pathways in transplantation, and how digital technology can inform this. The results of this will inform the grant application of a much larger study into the effects of prehabilitation in transplantation.

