### 6.1 Inclusion Criteria:

- Aged 18 years and over
- Live kidney donor or transplant recipient

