### 6.2 Exclusion Criteria:

[figure not shown]
- Deceased donor transplant recipient
- Patients unable to wear or tolerate the wearable device
- Unstable angina pectoralis, recent myocardial infarction, recent cerebrovascular accident, or new arrhythmia
- Patient declines or is unable to participate in the exercise programme
- Patient lacks capacity to give informed consent to participate in the trial
- Non-English language
- Patient has no access to a smart device to download the OURa/Withings Health Mate/Corsano Research Trials app

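### Section 13.21 claims a wider cardiac exclusion than the criteria in Section 6.2 apply

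*Protocol*

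**What the plan says.** The intervention is done at home: "Participants will undergo a 6 week, at home exercise programme prior to their procedure". Section 13.21 explains how the exercise risk is handled. It opens with "Risks to participants will be minimised by careful selection criteria" and continues with "Those at risk of cardiac ischaemia or arrhythmia are excluded from this study as participants will be undertaking unsupervised exercise". It then adds a baseline fitness questionnaire that sets the video level, and information on when to stop and when to call for help.

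The opening of Section 6 requires all inclusion criteria to be met, bars anyone who meets an exclusion criterion, and removes a participant if an exclusion criterion arises after enrolment. Apart from age, the inclusion criterion in 6.1 is "Live kidney donor or transplant recipient", with no cardiac condition attached. The single cardiovascular exclusion in 6.2 is "Unstable angina pectoralis, recent myocardial infarction, recent cerebrovascular accident, or new arrhythmia". A further general exclusion is "Patient declines or is unable to participate in the exercise programme".

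Section 11 advises participants who feel unwell while exercising to take their usual medication, "such as salbutamol inhaler or GTN spray if they are already prescribed them".

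**The concern.** Section 13.21 gives its own reason for the exclusion, namely that nobody supervises the exercise. That reason applies to stable as well as unstable cardiac disease. An ethics committee reading 13.21 would take it that anyone at risk of ischaemia or arrhythmia is kept out. A screener working from 6.2 would keep out only people whose condition is unstable, recent or new. If both are followed as written, the protection described to the approving body differs from the one applied at entry. The same list governs removal after enrolment, so the mismatch continues through the programme.

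**Working it through.** No figure is involved and no calculation applies, so the check is a comparison of the text.

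**Step 1: which text decides entry.** The opening of Section 6 makes the lists in 6.1 and 6.2 decisive. Section 13.21 describes an exclusion but sits outside those lists.

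**Step 2: apply each passage to the same people.**

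| Person | Under 6.2 | Under 13.21 |
|---|---|---|
| Unstable angina | Excluded | Excluded |
| Recent infarction | Excluded | Excluded |
| New arrhythmia | Excluded | Excluded |
| Recent stroke | Excluded | Not mentioned |
| Stable angina | Not excluded | Excluded |
| Older infarct | Not excluded | Excluded |
| Established arrhythmia | Not excluded | Excluded |

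The last three rows are the conflict. Section 13.21 does not define who counts as at risk, so its outer limit is unsettled, but these three cases fall within any ordinary reading. Section 6.2 gives no time window for recent or new, so the width of the gap also depends on how a screener reads those words.

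**Step 3: look for another stated rule that closes the gap.**
- The inclusion criteria add no cardiac restriction.
- The exclusion for declining or being unable to do the programme concerns ability and willingness. A person with stable angina may be able and willing.
- Withdrawal for safety or by investigator decision (6.4) acts only after enrolment and names no cardiac condition.
- The baseline questionnaire in 13.21 chooses the exercise level and is not said to exclude anyone.

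None of these delivers the exclusion that 13.21 states.

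**Step 4: place Section 11.** Its medication advice is conditional and gives GTN as an example. It therefore allows for a participant who already has that prescription. This fits 6.2, which does not bar such a person, and sits badly with 13.21. The sentence in 13.21 is the one out of line with the other two passages.

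**The case against.** The best defence is that 13.21 only summarises 6.2. It refers to selection criteria, which points back to Section 6, and it sets no eligibility rule of its own, so a screener has one list to follow. It is right that 6.2 is the operative list. But being at risk of a condition is materially wider than having it in unstable, recent or new form, and a summary that widens the exclusion misdescribes it.

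A second defence is that protection does not rest on selection alone. There are stop-exercise instructions, fortnightly calls that can lower the intensity (5.2), withdrawal for safety reasons and usual transplant-team monitoring (Section 10). This stands, and it rules out calling the cardiac exclusion the main protection, which the protocol does not do. These layers still do not make the statement in 13.21 true.

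A third is that the screening proforma and the separate risk assessment are not shown and may be stricter. That is possible. The finding is therefore limited to what the written criteria deliver and does not extend to what happens in clinic.

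A reader might also infer from Section 11 that the study expects to enrol GTN users. The wording does not support that. It is general advice with a condition attached, and it neither shows nor predicts that such people will take part. Nor are all three passages in mutual conflict, since 6.2 and Section 11 agree.

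**Conclusion.** The inconsistency is real. Section 13.21 states a cardiac exclusion that is wider than the one in 6.2, and no other stated rule makes up the difference. It should be corrected because 13.21 is part of the safety case for unsupervised home exercise.

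Its size in participants is unknown. The documents give no prevalence of stable or established cardiac disease in donors or recipients, and nothing in them supports an estimate.

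A reader might go further and infer that the feasibility results are compromised, because numbers screened and enrolled are listed outcomes (9.11). The effect there is minor. Each person whose eligibility turned on the difference would be 1 of 20 participants (1/20 = 5%) at the minimum size in 5.1, or 1 of 40 (1/40 = 2.5%) at the maximum, and these counts are only described. Section 9.2 says "Therefore, a power equation has not been used", so no sample size calculation is affected, and no analysis changes.

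The conclusion assumes that the exclusion list as shown is complete and that the unseen proforma follows it.

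**What to change.** Reconcile Sections 6.2, 11 and 13.21 so that one definition of cardiac exclusion is used throughout, and carry the same wording into the screening proforma. Which definition applies is a clinical and ethical decision for the investigators and the ethics committee, and this review takes no position on it. If the list in 6.2 is kept, 13.21 must stop saying that everyone at risk is excluded. If the statement in 13.21 is kept, 6.2 must be brought into line with it and Section 11 checked against the result. Any of the words recent, new or at risk that remain should be defined, so that two screeners reach the same answer.

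The cost is a protocol wording amendment and a matching check of the proforma. If the wider exclusion is chosen, the eligible pool may shrink by a number that the documents do not allow to be estimated.
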